### Details on AE reporting

A flag will indicate to which study phase an AE belongs to: before therapy, treatment period (initial treatment 3 mg/kg/week SC for 4 weeks, followed by 1.5 mg/kg/week SC) up-titration period, or follow up (general section 4.1).

All treated patients will be analyzed by descriptive summaries of the AEs by SOC mapped term (by descending frequency) and by Preferred Term (PT) (by descending frequency).

Multiple occurrences of the same AE (by PT) per subject are counted only once unless defined otherwise, this also applies for Bleeds which are reported as SAE. For Total number of Events multiple occurrences of the same AE on an individual are counted separately. Symptoms of Injection Site Reactions are summarized separately. For some specific adverse event types, an additional table will display instances where multiple occurrences of the same AE in the same patient are all counted (for Disclosure purposes).

A listing of AEs will be generated for patients with at least one up-titration. If at least 10 patients are up-titrated then a summary table will be produced on the period after up-titration.

A standard summary table is produced for AEs falling into SMQ-hemorrhage (wide).

#### **4.9.2.1 Adverse events of special interest**

Adverse Events of Special Interest (AESI) are defined as cases of:

1. Potential drug-induced liver injuries
2. Suspected transmission of an infectious agent by the study drug
3. Systemic hypersensitivity or anaphylactic or anaphylactoid reactions,
4. Thromboembolic events search.
5. TMA events

##### Notes:

The AESI categories and preferred terms to be summarised will be identified from the project level list which covers the categories defined for this study, if applicable; or based on the investigator's judgement as collected in the eCRF otherwise.

In addition, potential drug-induced liver injuries will have to meet the Hy's Law criteria, based on laboratory results:

- ALT or AST > 3 × baseline
- and
- Total bilirubin > 2 × ULN (of which ≥35% is direct bilirubin)

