### **5.2.3 Adverse Events of Special Interest (Immediately Reportable to the Sponsor)**

Adverse events of special interest are required to be reported by the investigator to the Sponsor immediately (i.e., no more than 24 hours after learning of the event; see [Section 5.4.2](#) for reporting instructions). Adverse events of special interest for this study include the following:

- Cases of potential drug-induced liver injury that include an elevated ALT or AST in combination with either an elevated bilirubin or clinical jaundice, as defined by Hy's law (see [Section 5.3.5.7](#))
- Suspected transmission of an infectious agent by the study drug, as defined below
- Any organism, virus, or infectious particle (e.g., prion protein transmitting transmissible spongiform encephalopathy), pathogenic or non-pathogenic, is considered an infectious agent. A transmission of an infectious agent may be suspected from clinical symptoms or laboratory findings that indicate an infection in a patient exposed to a medicinal product. This term applies only when a contamination of the study drug is suspected.
- Systemic hypersensitivity reactions and anaphylactic and anaphylactoid reactions (see Sampson's Criteria in [Appendix 4](#))
- Thromboembolic events
- Microangiopathic hemolytic anemia or TMA (e.g. hemolytic uremic syndrome).

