### **5.3.5.7 Abnormal Liver Function Tests**

The finding of an elevated ALT or AST ( $> 3 \times$  baseline value) in combination with either an elevated total bilirubin ( $> 2 \times$  ULN) or clinical jaundice in the absence of cholestasis or other causes of hyperbilirubinemia is considered to be an indicator of severe liver injury (as

defined by Hy's law). Therefore, investigators must report as an adverse event the occurrence of either of the following:

- Treatment-emergent ALT or AST > 3 x baseline value in combination with total bilirubin > 2 x ULN (of which  $\geq$  35% is direct bilirubin)
- Treatment-emergent ALT or AST > 3 x baseline value in combination with clinical jaundice.

The most appropriate diagnosis or (if a diagnosis cannot be established) the abnormal laboratory values should be recorded on the Adverse Event eCRF (see [Section 5.3.5.2](#)) and reported to the Sponsor immediately (i.e., no more than 24 hours after learning of the event), either as a serious adverse event or an adverse event of special interest (see [Section 5.4.2](#)).

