### 2.2.1 Adverse Events of Special Interest

Adverse events of special interest (AESI) for this study include the following:

- Cases of potential drug-induced liver injury that include an elevated ALT or AST in combination with either an elevated bilirubin or clinical jaundice, as defined by Hy's law (see Protocol Section 5.3.5.7).
- Suspected transmission of an infectious agent by the study drug, as defined below. Any organism, virus, or infectious particle (e.g., prion protein transmitting transmissible spongiform encephalopathy), pathogenic or non-pathogenic, is considered an infectious agent. A transmission of an infectious agent may be suspected from clinical symptoms or laboratory findings that indicate an infection in a patient exposed to a medicinal product. This term applies only when a contamination of the study drug is suspected.
- Systemic hypersensitivity reactions and anaphylactic and anaphylactoid reactions (see Sampson's Criteria in Protocol Appendix 4).
- Thromboembolic events.
- Microangiopathic hemolytic anemia or TMA (e.g. hemolytic uremic syndrome).

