#### **4.9.2 Adverse Events**

Definitions of adverse events can be found in the CSP in section 5.2.

The primary objective of this study is to evaluate the overall safety and tolerability of prophylactic administration of emicizumab in patients with congenital hemophilia A who

have persistent inhibitors against FVIII at enrollment. Of primary interest in this study are the incidence and severity of all adverse events, including thromboembolic events, microangiopathic hemolytic anemia or TMA, systemic hypersensitivity, anaphylaxis, and anaphylactoid events.

Overall summaries of adverse events, serious adverse events and local injection site reactions will be presented by the number and percentage of patients having any event, having a related event, having an event leading to modification/interruption of study treatment, having an event leading to discontinuation from study, having an event leading to study treatment withdrawal, having an AESI, having a fatal AE, having grade 3 and above event. The overall number of events will also be presented.

The incidence of AEs, SAEs, AEs grade 3 and above, AEs related to study treatment, SAEs related to study treatment, AEs leading to modification/interruption of study treatment, AEs leading to discontinuation of study, AESIs, local ISRs by injection and by highest grade, fatal AEs, AEs occurring immediately after injection and AEs occurring within 24 hours after injection will be summarized. The incidence of AEs will also be summarized by highest grade.

A patient with more than one occurrence of the same adverse event in a particular System-Organ Class (SOC) or adverse event category will be counted only once in the total of those experiencing adverse events in that particular SOC or adverse event category. Any missing severity, causality, or outcome will not be imputed and classed as unknown.

Patients who died will be listed together with the cause of death.

All other information collected (e.g. action taken) will be listed as appropriate.

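### SAP 4.9.2.1 omits the clinical-jaundice limb of the liver-injury AESI definition, so some protocol-defined cases are left out of the AESI count and table

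*SAP*

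**What the plan says.** Protocol 5.2.3 lists potential drug-induced liver injury as an AESI when there is "elevated ALT or AST in combination with either an elevated bilirubin or clinical jaundice", and refers to 5.3.5.7 for the criteria. Protocol 5.3.5.7 sets out two reportable findings. The laboratory limb is "Treatment-emergent ALT or AST > 3 x baseline value in combination with total bilirubin > 2 x ULN", with at least 35% of the bilirubin direct. The clinical limb is "Treatment-emergent ALT or AST > 3 x baseline value in combination with clinical jaundice", with no condition on any bilirubin value.

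SAP 2.2.1 repeats the protocol's alternative: "in combination with either an elevated bilirubin or clinical jaundice".

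The notes to SAP 4.9.2.1 say how AESIs will be picked out for the summaries. All five categories are identified from a project-level list where one applies, or "based on the investigator's judgement as collected in the eCRF otherwise". A further condition is then added for liver injury alone: "potential drug-induced liver injuries will have to meet the Hy's Law criteria, based on laboratory results". The two criteria listed under it are ALT or AST above 3 x baseline and total bilirubin above 2 x ULN (at least 35% direct), joined by an explicit and. Jaundice is not mentioned.

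SAP 2.2 places the analysis of AESIs under the primary objective. SAP 4.9.2 reports them twice: as a line in the overall AE summary and as a separate incidence summary.

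**The concern.** The SAP defines the same event in two ways. Section 2.2.1 follows the protocol, while 4.9.2.1, the section a programmer would implement, is narrower. Its wording states a necessary condition, so a case that the investigator correctly reported as an AESI through the jaundice limb would be overridden at analysis. No reason is given for dropping that limb. The SAP version history says only that the AESI list was revised to follow the protocol, which suggests that the omission was not intended.

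The laboratory rule is a strict subset of the protocol rule, so the difference can only lower the liver-injury AESI count. It can never raise it.

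**Working it through.** **Step 1. The two rules as logical conditions.** Let E be ALT or AST above 3 x baseline, B be total bilirubin above 2 x ULN with at least 35% direct, and J be clinical jaundice.

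- Protocol 5.3.5.7, and SAP 2.2.1 by reference to it: E and (B or J).
- SAP 4.9.2.1: E and B.

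The rules differ exactly where E and J hold and B does not.

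**Step 2. Hypothetical profiles, all with ALT at 4 x baseline.**

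| Bilirubin (x ULN) | Direct fraction | Jaundice | Protocol rule | SAP 4.9.2.1 rule |
|---|---|---|---|---|
| 2.5 | 50% | no | AESI | AESI |
| 2.5 | 50% | yes | AESI | AESI |
| 2.5 | 30% | yes | AESI | not an AESI |
| 1.9 | 50% | yes | AESI | not an AESI |
| no result | no result | yes | AESI | not an AESI |

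Three of the four jaundice profiles are lost. The fourth also meets the laboratory limb and is kept. These profiles show where the rules part; they say nothing about how often each would occur.

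**Step 3. The plan's own precision figures.** SAP 2.3, Table 1 gives Clopper-Pearson 95% limits at N = 200. With x events, the lower limit is the 0.025 quantile of Beta(x, 200 - x + 1) and the upper limit is the 0.975 quantile of Beta(x + 1, 200 - x).

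| x | Recomputed | SAP Table 1 |
|---|---|---|
| 5 | 0.82-5.74% | 0.8-5.7% |
| 10 | 2.42-9.00% | 2.4-9.0% |
| 20 | 6.22-15.02% | 6.2-15.0% |
| 30 | 10.35-20.72% | 10.4-20.7% |

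The table reproduces to rounding.

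**Step 4. Illustration of one lost case.** The same formula gives:

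- 1/200: estimate 0.5%, limits 0.01% and 2.75%.
- 0/200: estimate 0%, upper limit 1 - 0.025^(1/200) = 1.83%.

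One case of the kind in Step 1, among an assumed 200 treated patients, would move the liver-injury AESI line from the first result to the second.

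**Step 5. Where the event still appears.** The condition in 4.9.2.1 governs AESI classification only. SAP 4.9.2 summarises all treatment-emergent AEs by system organ class, preferred term and highest grade, with separate summaries of serious, grade 3 or above, related and fatal events. None of these carries the Hy's law filter. Protocol 5.3.5.7 requires such a case to be recorded as an AE and reported as an SAE or AESI, so it reaches those tables.

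**The case against.** The strongest reply is that little is lost. The endpoint is broad: "Of primary interest in this study are the incidence and severity of all adverse events". The events then named are thrombotic, microangiopathic and hypersensitivity events, and liver injury is not among them. The study is descriptive, the confidence intervals for AEs are optional, and the documents give no expected rate of liver injury. All of that stands. It limits the consequence but does not remove the contradiction, because SAP 2.2 puts AESIs as a class under the primary objective.

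Three stronger readings are tempting and should be set aside.

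- A reader might infer that the case disappears from the primary safety analysis. It does not: only the AESI line and the AESI table lose it.
- A reader might infer that every jaundice case is lost. Only those that also fail the bilirubin rule are. Protocol 4.5.6.1 puts total and direct bilirubin in the same chemistry panel as ALT and AST, so where the enzymes come from a full protocol panel a bilirubin result should accompany them. The missing-value route is therefore narrower than it first appears. The routes through bilirubin not above 2 x ULN, or a low direct fraction, are unaffected by this.
- A reader might infer that a bilirubin measured at a local laboratory excludes the case. SAP 4.9.2.1 asks for laboratory results, not central ones, and protocol 4.5.6 has additional results needed for the safety assessment recorded in the eCRF.

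It could also be said that Hy's law is a laboratory concept, so the SAP merely makes it operational. That fails on the documents: protocol 5.3.5.7 applies the Hy's law label to both limbs.

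One practical objection does stand. Protocol 5.3.5.2 tells sites to record a known diagnosis instead of its signs, with jaundice as one of its examples, so a jaundice term may be absent from the AE data. The fix has to allow for this.

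**Conclusion.** The point holds as a definitional error in SAP 4.9.2.1: it conflicts with protocol 5.2.3 and 5.3.5.7 and with SAP 2.2.1, and nothing elsewhere in the SAP restores the missing limb. Followed as written, the plan would misclassify a protocol-defined AESI whenever ALT or AST exceeds 3 x baseline with clinical jaundice and the bilirubin criterion is not shown to be met.

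The effect is confined to one AESI category and acts in one direction. Its size cannot be estimated from the documents; the change from 1/200 to 0/200 rests on one assumed case and an assumed 200 treated patients. The conclusion also takes the added condition at its plain meaning, as a requirement on top of the list or investigator route and not as an alternative to it. It should be corrected, since a case in such a sparse category should not depend on which section of the SAP was programmed.

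**What to change.** In the notes to SAP 4.9.2.1, state the liver-injury criterion as: ALT or AST > 3 x baseline AND (total bilirubin > 2 x ULN of which ≥ 35% is direct, OR clinical jaundice). Add that clinical jaundice is taken from the investigator's AE/AESI report in the eCRF, and not only from a jaundice preferred term. This brings 4.9.2.1 into line with SAP 2.2.1 and protocol 5.3.5.7.

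Leave the rule for identifying the other four AESI categories unchanged. Counting every event that is on the project list or flagged by the investigator would go too far: it would make the enzyme criterion redundant for liver injury and alter the other categories without a reason.

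The cost is one line of SAP text and no new data collection. The small downside is that the jaundice limb may need a brief case-level check of the investigator's report, because it cannot always be derived from coded AE terms.

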#### **4.9.3 Deaths**

Deaths are AEs with fatal outcomes and will be presented separately as described in section 4.9.2.

#### **4.9.4 Surgeries**

Surgeries and procedures during study conduct, collected on the eCRF page for "On-study Surgery and Related Hemophilia Medication Log", will be summarized in a frequency table, for the safety population.

In addition, the following analyses will be conducted on the Surgery population, for minor and major surgeries separately, and by surgery category (arthroplasty / CVADs / dental / joint / other).

Surgeries and procedures during study conduct will be summarized by PT.

Surgeries and procedures during study conduct, as well as hemophilia medications related to these surgeries (as collected on the BMQ) and occurrence of post-operative bleeds (treated and untreated), i.e. bleeds caused by a surgery or procedure, will be summarized. The surgery leading to a post-operative bleed will be identified as the last on-study surgery on or prior the start of the post-operative bleed.

The duration of exposure to emicizumab (in days) prior to the start of the surgery will be summarized.

The cumulative dose (dose/kg) of prophylactic hemophilia medications received by surgery, as well as the number of injections by surgery, will be summarized for each hemophilia medication separately. In the same manner, the number of infusions per post-operative bleed, the cumulative dose (dose/kg) by bleed and the duration of treatment (in days) will be summarized, for each hemophilia medication separately.

All on-study surgeries and prophylactic hemophilia medications as collected in the BMQ will be listed together. In addition, all on-study surgeries and prophylactic hemophilia medications as collected on the eCRF page for “Related Hemophilia Medications” will also be listed together.

An additional listing on post-operative bleeds and corresponding treatment for bleed will also be provided.

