#### 4.5.7.4 Definitions of Bleed Types

Bleed assessments will be separated into spontaneous bleeds, traumatic bleeds, and bleeds related to procedures. Both spontaneous bleeds (i.e., the occurrence of hemorrhage where neither the patient nor a caregiver can identify a reason) and traumatic bleeds (i.e., hemorrhage occurring secondary to an event such as trauma, “strenuous” activity, or “overuse”) will be collected. The definitions for the different type of bleeds are as follows:

- **Spontaneous bleeds.** Bleeds will be classified as spontaneous if a patient records a bleed when there is no known contributing factor such as definite trauma, antecedent “strenuous” activity, “overuse”, or procedure/surgery. The determination of what constitutes “strenuous” or “overuse” will be at the discretion of the patient. For example, light jogging may be considered “non-strenuous” while sprinting may be considered “strenuous”; lifting of weights for a short period of time may be considered “moderate use” while repetitive weightlifting may be considered “overuse”
- **Traumatic bleeds.** Bleeds should be classified as traumatic if a patient records a bleed when there is a known or believed reason for the bleed. For example, if a patient were to exercise “strenuously” and then have a bleed in the absence of any obvious injury, the bleed would be recorded as a traumatic bleed because, although no injury occurred, there was antecedent “strenuous” activity. Bleeds with preceding injuries would certainly be classified as traumatic. In addition, bleeds related to surgery, such as hematomas resulting from any surgeries, will also be classified as traumatic bleeds. Bleeds related to surgeries will not be associated with any trauma except surgery-induced trauma
- **Bleeds related to procedures.** This category would include hematomas resulting from any invasive procedure (e.g., tooth extractions, venepuncture, or SC drug administrations) or invasive diagnostic procedures (e.g., lumbar puncture, arterial blood gas determination, or any endoscopy with biopsy, etc.) or surgeries. Any instances of these bleeds would not be counted as bleeds in the context of the study, but the relevant

data will be collected. Bleeds related to procedures will not be associated with any trauma except procedure-induced trauma.

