### 2.2.2.6 Definitions of Cause/Classification of Bleeds

Bleed assessments will be separated into spontaneous bleeds, traumatic bleeds, and bleeds related to procedures. Both spontaneous bleeds (i.e., the occurrence of hemorrhage where neither the patient nor a caregiver can identify a reason) and traumatic bleeds (i.e., hemorrhage occurring secondary to an event such as trauma, “strenuous” activity, or “overuse”) will be collected. The definitions for the different type of bleeds are as follows:

- **Spontaneous bleeds.** Bleeds will be classified as spontaneous if a patient records a bleed when there is no known contributing factor such as definite trauma, antecedent “strenuous” activity, “overuse”, or procedure/surgery. The determination of what constitutes “strenuous” or “overuse” will be at the discretion of the patient. For example, light jogging may be considered “non-strenuous” while sprinting may be considered “strenuous”; lifting of weights for a short period of time may be considered “moderate use” while repetitive weightlifting may be considered “overuse”.
- **Traumatic bleeds.** Bleeds should be classified as traumatic if a patient records a bleed when there is a known or believed reason for the bleed. For example, if a patient were to exercise “strenuously” and then have a bleed in the absence of any

obvious injury, the bleed would be recorded as a traumatic bleed because, although no injury occurred, there was antecedent “strenuous” activity. Bleeds with preceding injuries would certainly be classified as traumatic. In addition, bleeds related to surgery, such as hematomas resulting from any surgeries, will also be classified as traumatic bleeds. Bleeds related to surgeries will not be associated with any trauma except surgery-induced trauma.

- **Bleeds related to procedures.** This category would include hematomas resulting from any invasive procedure (e.g., tooth extractions, venipuncture, or SC drug administrations) or invasive diagnostic procedures (e.g., lumbar puncture, arterial blood gas determination, or any endoscopy with biopsy, etc.) or surgeries. Any instances of these bleeds would not be counted as bleeds in the context of the study, but the relevant data will be collected. Bleeds related to procedures will not be associated with any trauma except procedure-induced trauma.

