#### **4.6.1.3 Cause, type and location of bleed**

Cause of bleed (spontaneous, traumatic, procedure/surgery) and location of bleed by bleed type (Joint, Muscle, other) will be summarized. The analysis will be performed separately for treated bleeds (with 72-hour rule) and all bleeds without applying the 72-Hour rule and including bleeds due to surgeries/procedures.

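### The SAP links procedure bleeds to the last on-study surgery with no time limit, so a later needle-site hematoma can be counted as a post-operative bleed

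*SAP*

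**What the plan says.** SAP 4.9.4 (Surgeries) summarizes, in the Surgery population, "post-operative bleeds (treated and untreated), i.e. bleeds caused by a surgery or procedure". Each such bleed is then assigned to a surgery: the one responsible "will be identified as the last on-study surgery on or prior the start of the post-operative bleed". The section gives no maximum interval, no requirement that bleed site and surgical site agree, and no adjudication step. The linked bleeds feed summaries of bleed occurrence and, for each hemophilia medication, of infusions, cumulative dose per kg and treatment duration per post-operative bleed. All are produced separately for minor and major surgery and by surgery category.

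The procedure category is defined in SAP 2.2.2.6 as covering "hematomas resulting from any invasive procedure (e.g., tooth extractions, venipuncture, or SC drug administrations", among other procedures and surgeries. Protocol 4.5.7.4 has the same definition. SAP 4.6.1.3 reports cause of bleed with procedure and surgery as a single combined level.

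The Surgery population (SAP 4.2.5) requires only one emicizumab dose and one on-study surgery. SAP 4.9.4 ends with a listing of post-operative bleeds and their treatment, but gives no rule for breaking a link that the listing shows to be implausible.

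**The concern.** The rule has two features that cause trouble together. The pool of bleeds includes bruises from ordinary needle sticks, and untreated bleeds count, so a trivial hematoma needs no factor treatment to enter. The link then reaches back without limit to the last operation. A patient with a tooth extraction in Month 2 who records an injection hematoma as a procedure bleed in Month 14 would appear in the table as having bled after the extraction.

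Protocol 1.2.2.6 says that emicizumab has not been specifically tested in patients undergoing surgery and that the available data are limited, so readers are likely to consult these summaries. Split by minor/major status and by category, some cells may hold few surgeries, and one or two false links could change them. Surgeries early in follow-up have more injections after them and so more chance of a false link, which would also disturb comparisons between surgery categories.

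**Working it through.** **1. The rule applied literally.** The plan states no figure for post-operative bleeds, so there is none to reproduce. Take a patient with one surgery on day 100. Procedure-cause bleeds on day 101 and on day 700 are both linked to day 100. With surgeries on days 100 and 400, a bleed on day 399 is linked to day 100. Elapsed time never breaks a link.

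**2. What is and is not touched.** SAP 2.2.2.2 and 2.2.2.4 exclude bleeds due to surgery/procedure from treated bleeds and from all bleeds, so the annualized bleed rates are unaffected. The primary endpoint is the incidence and severity of adverse events, which does not use this link. The effect is confined to the SAP 4.9.4 surgery summaries.

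**3. Inputs for an approximate size.**
- Injections: weekly for two years, about 104. A surgery at week 52 leaves 52; a surgery at week 26 leaves 78.
- Injection-site reactions (ISRs): 35 of 189 patients (18.5%), median exposure 38 weeks (protocol 1.2.2.3).
- Commonest ISR symptoms, same section: erythema 7.4%, pruritus 5.3%, pain 5.3%. Hematoma is not among them.
- Assumption A: hematoma affects at most 5.3% of patients over 38 weekly doses, with constant risk per dose.
- Assumption B: a fraction f of these hematomas is also entered in the bleed record as procedure/surgery. The documents give no value for f.

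**4. Risk per dose.** p = 1 − (1 − 0.053)^(1/38) = 0.00143, or 0.14%.

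**5. Chance of at least one false link after a surgery**, 1 − (1 − f·p)^n:

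| f | n = 52 | n = 78 |
|---|---|---|
| 10% | 0.7% | 1.1% |
| 50% | 3.7% | 5.4% |
| 100% | 7.2% | 10.6% |

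These figures leave out blood draws. About 2 scheduled draws follow a week-52 surgery and about 4 follow a week-26 surgery. If a draw carried the same risk as an injection (a further assumption), the last row would become 7.4% (n = 54) and 11.1% (n = 82).

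**6. Extreme case.** If every ISR of any kind were a hematoma entered as a procedure bleed, p = 1 − (1 − 35/189)^(1/38) = 0.54%, giving 24% (n = 52) and 34% (n = 78). The reported symptom profile does not support this.

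**7. Effect of a window.** With a window holding about 4 weekly injections (28 days, for illustration only), Assumption A and f = 100% give 1 − (1 − 0.00143)^4 = 0.6%, in place of 7.2% or 10.6%.

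**The case against.** The strongest reply is that injection hematomas already have their own route. Protocol 5.1.1.1 lists injection-site hematoma among local ISRs, and protocol 5.3.5.1 and the adverse-event footnote to Appendix 1 send ISR details to a dedicated form. Nothing shows that patients routinely enter the same bruise in the bleed record as well. This stands. A reader might infer that later bruises will be reported as surgical bleeding; the documents support only that they can be, for patients with an earlier on-study surgery and for hematomas entered with cause procedure/surgery.

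A reader might also infer that the tables must overstate post-operative bleeding. The false links add bleeds, but the net direction is not settled. SAP 2.2.2.6 and protocol 4.5.7.4 also say that bleeds related to surgery are classed as traumatic, while listing surgeries under the procedure category. If true surgical bleeds are recorded as traumatic, they could drop out of the post-operative tables and produce an understatement.

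A third inference, that a quarter or a third of surgery patients could be affected, needs nearly every ISR to be a hematoma entered twice, and the ISR figures make that implausible. Nor are surgical results a main product of this trial: no objective or endpoint concerns surgery, and all analyses are descriptive.

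The closing listing would let a careful reader spot a late link case by case, but it does not correct the summary tables.

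**Conclusion.** The point holds for the surgery summaries. The rule as written is more than a missing detail: applied literally, it can assign a needle-site hematoma to an operation many months earlier, and nothing elsewhere in the protocol or SAP prevents this. The size is unknown. About 7% of surgery patients with 52 later doses and 11% with 78 is an upper figure that rests on Assumption A and on every hematoma being entered as a procedure bleed; with 10% entry it is about 1%. Blood draws would add to either figure by an amount for which the documents give no rate. The absence of a time limit and the breadth of the category are certain from the text. The frequency of false links and the net direction of bias are not.

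**What to change.** In SAP 4.9.4:

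- Link a procedure/surgery bleed to a logged surgery or procedure only if it starts within a pre-specified window after it, and state why that length was chosen. The 28 days used above is only an illustration.
- Report procedure bleeds outside the window in a separate row, not attributed to any surgery, so that no bleed is lost.
- Exclude SC-injection and venipuncture hematomas where the bleed record identifies them. The documents do not show that it does, and a date filter cannot make this distinction. If it does not, say so and rely on the window, accepting that needle-site hematomas inside it remain.
- Reconcile the wording of SAP 2.2.2.6, which places surgery-related bleeds under both traumatic and procedure bleeds, and state which recorded causes enter the post-operative tables.

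The cost is a short SAP edit and a filter on dates already collected. The SAP already uses time rules of this kind: 72 hours for merging bleeds, and −7 to +30 days for associating adverse events with COVID-19. The downside is that a true late surgical bleed would move to the separate row, where it stays visible.
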